9.5 Analysis of secondary variables

9.5.1 Efficacy variables

The secondary efficacy variables are the following:

1. Dactylitis (yes, no)

[figure not shown]
2. Enthesitis (yes, no)
3. ACR50 response (yes, no)
4. ACR70 response (yes, no)
5. Minimal Disease Activity (yes, no)
6. PASI75 response (yes, no)
7. PASI90 response (yes, no)
8. PASI100 response (yes, no)
9. Change from baseline in DAS28-CRP
10. Change from baseline in PASDAS
11. Change from baseline in SF12
12. Change from baseline in HAQ-DI

[figure not shown]
Two analyses of dactylitis and enthesitis (secondary efficacy variables 1 and 2) will be performed at each time point. For the first analysis, the data for the subgroup of patients who have dactylitis at baseline will be used (similarly for enthesitis) and the analysis of the binary response variable (yes, no) will be similar to the analysis of secondary efficacy variables 3-8 below. In the supporting analysis, the data for all patients will be used and an ordinal variable will be created based on presence (yes) or absence (no) of dactylitis at baseline and a post-baseline visit (similarly for enthesitis). The three categories for the ordinal variable will be no/no (category 1), no/yes and yes/no (category 2), and yes/yes (category 3). This ordinal response variable will be analyzed using a proportional odds regression model with treatment (3 treatment groups), methotrexate usage at baseline (yes, no), and body weight as explanatory variables (Stokes, Davis, and Koch, 2012). The odds ratios for each dose of secukinumab versus placebo, 95% confidence intervals for the odds ratios, and p-values based on the fitted model will be reported.

Secondary efficacy variables 3-8 will be analyzed at each time point using a logistic regression model with treatment (3 treatment groups), methotrexate usage at baseline (yes, no), and body weight as explanatory variables (Stokes, Davis, and Koch, 2012). The odds ratios for each dose of secukinumab versus placebo, 95% confidence intervals for the odds ratios, and p-values based on the fitted model will be reported.

Secondary efficacy variables 9-12 will be analyzed at each time point by an analysis of covariance (ANCOVA) model with treatment (3 treatment groups), baseline, methotrexate usage at baseline (yes, no), and body weight as explanatory variables. The least squares means of the three treatment groups, least squares mean differences between each dose of secukinumab and placebo, 95% confidence intervals for the difference between each dose of secukinumab and placebo, and p-values based on the fitted linear model will be reported. Missing data will be imputed using the last-observation-carried-forward (LOCF) method.

Analyses of the secondary efficacy variables will be based on the Full Analysis Set.

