2.7.2 Statistical hypothesis, model, and method of analysis

Dactylitis and enthesitis

Analyses of dactylitis and enthesitis will be performed at each time point up to Week 16. The data for the subgroup of patients who have dactylitis at baseline (similarly for enthesitis) will be used and the data will be analyzed using a logistic regression model with treatment (3 treatment groups), methotrexate usage at baseline (yes, no), and body weight as explanatory variables. The odds ratios for each dose of secukinumab versus placebo, 95% confidence interval for the odds ratios, and p-values based on the fitted model will be reported.

Number and percentages of patients with presence of enthesitis will be reported for each treatment group and by visit in entire treatment period up to Week 52. Similar summary will be provided for patients with presence of enthesitis using non-responder imputation.

The above analyses will be done on Dactylitis Subset,

ACR20, ACR50, and ACR70 responses

ACR20, ACR50, ACR70 responses at each time point up to Week 16, and in subsets of patients with active PsA and number of tender and swollen joints < 10 and ≥ 10 at baseline will be analyzed using a logistic regression model with treatment (3 treatment groups), methotrexate usage at baseline (yes, no), and body weight as explanatory variables. The odds ratios for each dose of secukinumab versus placebo, 95% confidence intervals for the odds ratios, and p-values based on the fitted model will be reported.

Additionally, ACR50 and ACR70 responses will be analyzed as analogous to primary efficacy variable at each time point up to Week 16.

Number and percentages of ACR50 and ACR70 responders will be reported for each treatment group, concomitant methotrexate usage at baseline and by visit in entire treatment period up to Week 52. Similar summary will be provided for ACR50 and ACR70 using non-responder imputation.

Number and percentages of ACR50 and ACR70 responders in subsets of patients with active PsA and number of tender and swollen joints < 10 and \geq 10 at baseline will be reported for each treatment group and by visit in entire treatment period up to Week 52. Similar summary will be provided for ACR50 and ACR70 using non-responder imputation.

Minimal Disease Activity

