2.7.4 Supportive analyses

Not applicable.

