2.14 Interim analysis

The database of this study will be locked twice, first after the end of Treatment Period 1 (Week 16) and again after the end of Treatment Period 2 (Week 52). Data analyses will follow after database lock at Week 16. The main analysis for the primary objective will be done at Week 16. As Week 16 is the primary analysis time point, no adjustment to the significance level of 0.05 will be made.

3 Sample size calculation

The sample size was calculated based on the primary efficacy variable (i.e., ACR20 response) for the primary comparison (i.e., secukinumab 300 mg versus placebo). ACR20 response rates of 50% for secukinumab 300 mg and 20% for placebo (corresponding to an Odds ratio of 4) at Week 16 were assumed, based on results from AIN457F2312 (FUTURE 2) study. Using a continuity-corrected chi-squared test, an allocation ratio of 2:1, a two-sided significance level of 0.05, and a power of 0.90, approximately 88 patients in secukinumab 300 mg group and 44 patients in placebo group will be needed.

Assuming a loss to follow-up rate of 10% and a 2:2:1 allocation ratio (secukinumab 300 mg: secukinumab 150 mg: placebo), the total number of randomized patients will be approximately 250 (100 on secukinumab 300 mg, 100 on secukinumab 150 mg, and 50 on placebo).

The sample size estimation was done using query Advisor 7.0.

4 Change to protocol specified analyses

Not applicable.

5 Appendix

This section will be used later for drafting CSR Appendix 16.1.9.

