5.4.3 Secondary analysis

Categorical variables will be analyzed using the logistic model, using the code described above.

Continuous variables will be analyzed using an analysis of covariance (ANCOVA) model with treatment, baseline value, methotrexate usage at baseline (yes, no), and body weight as explanatory variables.

Proc mixed data=aaa order=internal; Class TRT MTX; Model change=TRT MTX BLV weight/ ddfm=kr; Lsmeans TRT/ cl diff; Contrast "sec300 vs plb" TRT 1 0 -1/ cl diff alpha=0.05; Contrast "sec150 vs plb" TRT 0 1 -1/ cl diff alpha=0.05; Run;

For supportive analysis using Cochran-Mantel-Haenszel (CMH) test to compare treatments adjusting for methotrexate usage at baseline, the same code will be used as described above.

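### The protocol's supporting all-patient analysis of dactylitis and enthesitis builds baseline status into the outcome without adjusting for it, and the visible SAP omits the analysis while declaring no change

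*Protocol*

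**What the plan says.** Protocol 9.5.1, and the Data analysis part of the protocol summary, plan two analyses of each sign.

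- **First analysis.** A binary logistic model in patients who have the sign at baseline: "For the first analysis, the data for the subgroup of patients who have dactylitis at baseline will be used (similarly for enthesitis"). This matches the secondary objectives in Protocol 2.2.
- **Supporting analysis.** "In the supporting analysis, the data for all patients will be used and an ordinal variable will be created" from baseline and post-baseline presence, coded "no/no (category 1), no/yes and yes/no (category 2), and yes/yes (category 3"). It is fitted by a "proportional odds regression model with treatment (3 treatment groups), methotrexate usage at baseline (yes, no), and body weight as explanatory variables". Baseline presence of the sign is not in that list, although the ANCOVA models for the continuous secondary variables in the same section do include baseline.

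SAP 2.7.2 carries only the first of these: "The data for the subgroup of patients who have dactylitis at baseline (similarly for enthesitis) will be used", with logistic regression. The section "2.7.4 Supportive analyses" is marked not applicable. For modelling, SAP 5.4.3 says "Categorical variables will be analyzed using the logistic model, using the code described above", and otherwise gives ANCOVA and a reference to the CMH code. SAP Section 1 says that deviations from the protocol are documented. Section 4, "Change to protocol specified analyses", is marked not applicable.

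**The concern.** Write the sign as 0 or 1 at each visit. The score is then 1 + baseline + follow-up. Treatment cannot change the baseline term, yet that term adds as much to the score as follow-up does. With no baseline covariate, and no stratification at randomization (SAP 1.1), any chance difference in baseline prevalence between arms passes straight into the estimated treatment effect. Patients who never had the sign rank best whatever they received.

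The score also places a patient whose dactylitis resolves beside one who newly develops it, so an odds ratio on this scale has no clear clinical meaning.

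At stake is the only planned inferential analysis of these signs that uses all patients. If run, it could disagree with the baseline-positive analysis for no clinical reason. If it was dropped, the SAP should say so.

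**Working it through.** **Plan's own figure.** The documents give none for this analysis. The sample size for ACR20 (50% v 20%, 2:1, two-sided 0.05, power 0.90, continuity-corrected) reproduces as 88 and 44. Dividing by 0.9 gives 98 and 49, and 98 + 98 + 49 = 245, stated as about 250. Only the arm sizes of 100 and 50 are used below.

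**Assumed inputs.** The documents give no prevalence, resolution or onset rates for either sign. Assumed: resolution r = 50% active v 25% placebo; new onset o = 5% v 10%; baseline prevalence q = 30 to 90%.

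**Category probabilities.** P1 = (1 − q)(1 − o); P2 = (1 − q)o + qr; P3 = q(1 − r). At q = 0.5:

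- Active: 0.475, 0.275, 0.250
- Placebo: 0.450, 0.175, 0.375
- Odds ratio for category 2 or above: (0.525/0.475)/(0.550/0.450) = 0.90
- Odds ratio for category 3: (0.250/0.750)/(0.375/0.625) = 0.56
- Odds ratio for presence in baseline-positive patients: (0.50/0.50)/(0.75/0.25) = 0.33

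The lower cut barely responds to treatment, so proportional odds also fails under these rates.

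**How far chance imbalance moves the score (q = 0.5).**

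- Effect on the mean score: 0.5 × (0.25 − 0.50) + 0.5 × (0.05 − 0.10) = −0.15.
- One extra baseline-positive patient raises that patient's expected score by 1 + (1 − r) − o, which is 1.45 on active and 1.65 on placebo.
- Variance from baseline imbalance: 0.25 × (1.45²/100 + 1.65²/50) = 0.0189, SD 0.137.
- Remaining variance: 0.14875/100 + 0.13875/50 = 0.0043.
- Share due to imbalance: 0.0189/(0.0189 + 0.0043) = 81 to 82%.

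One SD of chance imbalance (0.137) is nearly as large as the whole treatment effect (0.15).

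**Power.** 40,000 simulated trials per row, 100 v 50, two-sided 0.05, counted when in favour of active. The ordinal variable was tested by the tie-corrected Wilcoxon test, the score-test equivalent of proportional odds. The other two columns use Mantel-Haenszel tests. Methotrexate and weight were left out.

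| Baseline prevalence | Ordinal OR (baseline-positive OR 0.33) | Ordinal, all patients | Baseline-positive analysis | All patients, stratified by baseline | Variance of ordinal statistic due to baseline imbalance |
|---|---|---|---|---|---|
| 30% | 0.79 | 10% | 35% | 46% | 82% |
| 50% | 0.74 | 15–16% | 55% | 60–61% | 83% |
| 70% | 0.62 | 31% | 70% | 73% | 71% |
| 90% | 0.44 | 64% | 81% | 82% | 38% |

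For the stratified test, imbalance explains under 1% of the variance. Despite the true benefit, the ordinal statistic points the wrong way in about 26, 19, 8 and 1% of trials.

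**Which feature causes the loss.**

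- Set new onset to zero in both arms, so that nothing is merged. At q = 0.5, power is still only 11% against 55% in the baseline-positive analysis.
- Split the merged category (no/no, yes/no, no/yes, yes/yes) but leave baseline unadjusted. Power is 12, 18, 34 and 65%, hardly better.
- Keep the protocol's coding but stratify by baseline. Power returns to the stratified column, because within each baseline stratum the lower category is always the better outcome (1 v 2, or 2 v 3).

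The cause is the unadjusted baseline component.

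**The case against.** **Only a supporting analysis is affected.** This stands. The secondary objectives are defined in patients with the sign at baseline, and the first analysis answers them. A reader might infer that the planned dactylitis and enthesitis conclusions are compromised; the documents do not support that.

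**The gain over what is already planned is small.** This stands too. Against the baseline-positive analysis, the adjusted all-patient analysis gains about 11 points of power at 30% prevalence and about 1 point at 90%. The large gap is only between the ordinal and the adjusted all-patient analyses.

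**The size depends on assumed rates.** A reader might infer that most of the treatment signal is always lost. Across the range of rates tried, the ordinal model keeps about 6 to 51% of the baseline-positive log odds ratio at prevalences of 20 to 70%, but 55 to 62% at 80% and 74 to 79% at 90%. Enthesitis counts if any one of 18 sites is positive (Protocol 6.4.12), so high prevalence cannot be ruled out.

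**Scoring onset and resolution alike may look like the cause of the loss.** The zero-onset check shows that it is not. It remains a fault of interpretation.

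**No bias or inflated type I error is shown.** Correct: under randomization the imbalance averages out over trials. The harm is noise in the one trial that is run.

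**The visible SAP already leaves the model out.** True, so the harm arises only if the protocol analysis is run. That does not cure the mismatch with Section 4. The SAP update log cites a Section 2.13 that is absent from the public text, so an ordinal analysis there cannot be excluded, although 2.7.4 and 5.4.3 point against it.

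**Conclusion.** The point holds for a supporting analysis. The ordinal model treats a pre-treatment value as part of the outcome and does not adjust for it. Under the assumed rates, chance baseline imbalance accounts for 71 to 83% of the variance of its test statistic at prevalences of 30 to 70%, falling to 38% at 90%. Its power is below that of the simpler analysis already planned first at every prevalence in the table. The power figures rest on assumed rates, two arms at a time, without methotrexate or weight. The structural fault does not depend on them.

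Separately, and needing no assumed rates, the visible SAP omits a protocol-specified analysis while Section 4 reports no change, subject to the missing Section 2.13. A reader might infer from this that the flawed model will be run; the documents leave that open.

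**What to change.** Replace the proportional-odds model with a logistic model of follow-up presence (yes, no) in all patients, with treatment, baseline presence of the sign, methotrexate use and body weight. Keep it as supporting and leave the baseline-positive analysis as it is. State how missing follow-up is scored in patients without the sign at baseline, because the non-responder rule in SAP 2.7.3 could count a dropout there as a new onset.

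The visible SAP updates of November and December 2018 are marked as made after the Week 16 database lock, when the analysts were to be unblinded (SAP 2.1). If the model is added after that lock, label it post hoc. If no all-patient analysis is wanted, dropping the ordinal model is acceptable.

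Either way, record in SAP Section 4 that the protocol's ordinal analysis was replaced or dropped, and why. The cost is SAP wording and at most one model per sign at each time point; no new data are needed.

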9.5.2 Safety variables

The assessment of safety will be based mainly on the frequency of adverse events and laboratory data. Other safety data (e.g., vital signs and special tests) will be considered, as appropriate.

Adverse events will be summarized by presenting, for each treatment group, the number and percentage of patients having any adverse event, having an adverse event in each body system and having each individual adverse event. Any other information collected (e.g., severity or relatedness to study medication) will be listed, as appropriate.

Adverse events and serious adverse events up to and including Week 16 visit will be included in the database for the analysis at the primary analysis time point (Week 16). All Adverse events and serious adverse events will be included in the final database analysis (Week 52).

Laboratory variables will be summarized.

Analysis of safety data will be based on the Safety Set.

9.6 Interim analyses

The database of this study will be locked twice, first after the end of Treatment Period 1 (Week 16) and again after the end of Treatment Period 2 (Week 52). Data analyses will follow each database lock. The main analysis (or test) for the primary objective will be done at Week 16. As Week 16 is the primary analysis time point, no adjustment to the significance level of 0.05 will be made.

9.7 Sample size calculation

The sample size was calculated based on the primary efficacy variable (i.e., ACR20 response) for the primary comparison (i.e., secukinumab 300 mg versus placebo). ACR20 response rates of 50% for secukinumab 300 mg and 20% for placebo (corresponding to an odds ratio of 4) at Week 16 were assumed, based on results from AIN457F2312 (FUTURE 2) study. Using a continuity-corrected chi-squared test, an allocation ratio of 2:1, a two-sided significance level of 0.05, and a power of 0.90, approximately 88 patients in secukinumab 300 mg group and 44 patients in placebo group will be needed (nQuery Advisor 7.0). Assuming a loss to follow-up rate of 10% and a 2:2:1 allocation ratio (secukinumab 300 mg: secukinumab 150 mg: placebo), the total number of randomized patients will be approximately 250 (100 on secukinumab 300 mg, 100 on secukinumab 150 mg, and 50 on placebo)

10 Ethical considerations

10.1 Regulatory and ethical compliance

This clinical study was designed and shall be implemented and reported in accordance with the ICH Harmonized Tripartite Guidelines for Good Clinical Practice, with applicable local regulations (including European Directive 2001/20/EC, US CFR 21, and Japanese Ministry of Health, Labor, and Welfare), and with the ethical principles laid down in the Declaration of Helsinki.

10.2 Informed consent procedures

Eligible patients may only be included in the study after providing written (witnessed, where required by law or regulation), IRB/IEC-approved informed consent, or, if incapable of doing so, after such consent has been provided by a legally acceptable representative(s) of the patient. In cases where the patient's representative gives consent, the patient should be informed about the study to the extent possible given his/her understanding. If the patient is capable of doing so, he/she should indicate assent by personally signing and dating the written informed consent document or a separate assent form. Informed consent must be obtained

before conducting any study-specific procedures (i.e. all of the procedures described in the protocol). The process of obtaining informed consent should be documented in the patient source documents.

Novartis will provide to investigators in a separate document a proposed informed consent form that complies with the ICH GCP guideline and regulatory requirements and is considered appropriate for this study. Any changes to the proposed consent form suggested by the investigator must be agreed to by Novartis before submission to the IRB/IEC and a copy of the approved version must be provided to the Novartis monitor after IRB/IEC approval.

Women of child bearing potential should be informed that taking the study treatment may involve unknown risks to the fetus if pregnancy were to occur during the study and agree that in order to participate in the study they must adhere to the contraception requirement for the duration of the study. If there is any question that the patient will not reliably comply, they should not be entered in the study.

10.3 Responsibilities of the investigator and IRB/IEC

Before initiating a trial, the investigator/institution should obtain approval/favorable opinion from the Institutional Review Board/Independent Ethics Committee (IRB/IEC) for the trial protocol, written informed consent form, consent form updates, subject recruitment procedures (e.g., advertisements) and any other written information to be provided to patients. Prior to study start, the investigator is required to sign a protocol signature page confirming his/her agreement to conduct the study in accordance with these documents and all of the instructions and procedures found in this protocol and to give access to all relevant data and records to Novartis monitors, auditors, Novartis Quality Assurance representatives, designated agents of Novartis, IRBs/IECs, and regulatory authorities as required. If an inspection of the clinical site is requested by a regulatory authority, the investigator must inform Novartis immediately that this request has been made.

10.4 Publication of study protocol and results

Novartis assures that the key design elements of this protocol will be posted in a publicly accessible database such as clinicaltrials.gov. In addition, upon study completion and finalization of the study report the results of this trial will be either submitted for publication and/or posted in a publicly accessible database of clinical trial results.

11 Protocol adherence

This protocol defines the study objectives, the study procedures and the data to be collected on study participants. Additional assessments required to ensure safety of patients should be administered as deemed necessary on a case by case basis. Under no circumstances should an investigator collect additional data or conduct any additional procedures for any research related purpose involving any investigational drugs.

Investigators ascertain they will apply due diligence to avoid protocol deviations. If an investigator feels a protocol deviation would improve the conduct of the study this must be considered a protocol amendment, and unless such an amendment is agreed upon by Novartis

and approved by the IRB/IEC and health authorities, where required, it cannot be implemented. All significant protocol deviations will be recorded and reported in the CSR.

12.1 Appendix 1: Clinically notable laboratory values and vital signs

The following criteria will be used to define expanded limits and notable abnormalities of key laboratory tests. Whether or not any action needs to be taken to address notable laboratory or vital signs values will be determined by the investigator/qualified site staff, taking into

account the overall status of the subject. No specific action is pre-defined within this study protocol.

Liver function and related variables

ALT (SGPT)	> 3 x Upper Limit of Normal (ULN)
AST (SGOT)	> 3 x ULN
Total bilirubin	> 1.5 x ULN
Alkaline phosphatase	> 2 x ULN

Renal function and electrolyte variables

Creatinine (serum)	> 1.5 x ULN
--------------------	-------------

Hematology values

Hemoglobin	≥ 2.0 g/dL decrease from baseline
Platelet count	< Lower Limit of Normal (LLN)
White blood cell	< 0.8 x LLN
Neutrophils	< 0.9 x LLN
Eosinophils	> 1.1 x ULN
Lymphocytes	> 1.1 x ULN

